7.6 Sample size

Based on the assumptions that the margin of error is 5%, the confidence level is 95%, the response distribution is 50%, and the prevalence of adherence to medication is 92.5%, the sample size for our study is 117. These assumptions are used to determine the sample size required to estimate a population parameter with a certain level of precision. The prevalence of adherence to medication (92.5%) was taken from a study conducted at Shahid Gangalal National Heart Centre in 2018, which reported that 92.5% of respondents were highly adherent to medication, as measured by the Morisky, Green, and Levine (MGL) scale 4-item questionnaire.

The sample size (n) is calculated according to Cochran's formula: $n = [z^2 * p * q / d^2]$

Where: z = 1.96 for a confidence level (α) of 95%, p = proportion (expressed as a decimal), d = margin of error and adding a 10% non-response rate by using the following formula:

$z = 1.96$, $p = 0.925$, $d = 0.05$

$n = [1.96^2 * 0.924 * (1 - 0.817) / (0.05)^2] = 106.39$

$n \approx 106$

The sample size needed for the study is 106 participants. By adding 10% non-response, the sample size is increased to 117 participants.

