ADHERENCE TO SECONDARY PREVENTION MEDICATIONS AND FACTORS INFLUENCING ADHERENCE, AFTER ACUTE CORONARY SYNDROME (ACS) IN PATIENTS ATTENDING A TERTIARY CARE CENTRE OF NEPAL: A DESCRIPTIVE CROSS SECTIONAL STUDY

2. Project summary (~250 words)

This study aims to assess adherence to secondary prevention medications among patients in Nepal following an Acute Coronary Syndrome (ACS) event and identify factors affecting adherence. ACS, a major cause of morbidity and mortality globally and in Nepal, requires effective secondary prevention to minimize recurrent cardiovascular events. However, adherence to prescribed medications remains low, especially in low- and middle-income countries like Nepal. Poor adherence can lead to increased healthcare burden, worsened patient outcomes, and higher mortality rates. To address this, the study will evaluate patients' medication adherence through the MYMEDS questionnaire, a self-reported tool, which has been positively received for its simplicity and clarity.

Conducted at the Manmohan Cardiothoracic Vascular and Transplant Centre in Nepal, the study will involve a sample of adult patients readmitted or attending follow-ups post-ACS. Convenience sampling will be used, targeting approximately 117 patients to account for non-responses. The research will gather data on patient demographics, socioeconomic factors, clinical characteristics, and self-reported adherence barriers, analyzing these with SPSS to assess correlations with clinical outcomes.

The expected 12-month project will consist of phases for ethical approvals, data collection, analysis, and report dissemination. By identifying key barriers to adherence, the study aims to inform targeted interventions that could enhance medication adherence, improve long-term cardiovascular outcomes, and reduce healthcare burdens in Nepal and other similar settings.

3. Introduction

Patients experiencing myocardial infarctions (MI) are at risk of subsequent cardiovascular events and prevention of recurrent events is a major clinical and public health priority (1).

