Pharmacological therapy plays a key role in the secondary prevention of CVD and improve long term outcomes particularly in patients who have not undergone revascularization via percutaneous coronary intervention (PCI) (2–4). Large evidence supports drugs conferring mortality benefit from several different classes: antiplatelet agents, angiotensin-converting enzyme inhibitors (ACEIs)/angiotensin receptor blockers (ARBs), beta blockers and lipid-lowering drugs (5–7).

Adherence to secondary prevention medications following acute coronary syndromes (ACS) is a predictor of future major adverse cardiovascular events. Medication usage (and its success) requires the coordination of the behaviours of both treating physicians and patients, particularly with regards to adherence. Underutilisation of these medications is associated with higher risk of major adverse cardiovascular events globally (8). Patients' poor adherence to their medication is a complex problem for health care services, especially in the care of heart diseases, for which the correct and effective treatment is essential for a patient's quality of life and survival rate(9). A study had shown that patients who recently experienced a myocardial infarction (MI) and did not adhere closely to their prescribed regimen were 2.6 times more likely to die within a year following the MI compared with those who followed their regimen more closely (10).

Medication adherence has been studied extensively over the past decades. Numerous reports in the literature had estimated that by 12 months, adherence to cardioprotective therapy had dropped to less than 50% across several classes of drugs including statins and ACE-Inhibitors(11). Some of the predictors of non-adherence most often cited include polypharmacy, frequency of medication changes, socioeconomic status, cost, household composition, comorbidity, and accessibility to medical care (12). Gaining an understanding of the key factors that influence adherence among patients post-ACS may allow treating physicians to tailor their treatment approach and implement effective hospital interventions to improve patient adherence and, subsequently, CV outcomes(13).

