7.5 Sampling method

In our research study, we will employ convenience sampling. Convenience sampling is a non-probability method where units are selected for inclusion in the sample because they are the easiest for the researcher to access. The target population consists of adult patients (age ≥ 18 years) who have either come to OPD for follow-up or have been readmitted in hospital for having cardiac complications months after surviving ACS (including STEMI, NSTEMI, and unstable angina). Rather than applying specific

stratification based on cancer type, we will approach patients who are readily available within the hospital setting. We will use the MYMEDS questionnaire. The researcher will personally ask all the questions and fill out the questionnaire for each eligible patient. To assess the socioeconomic status of participants, we will utilize the Modified Kuppuswamy's Socioeconomic Status Scale, adapted to the context of Nepal (18). Alongside demographic information such as gender, age at diagnosis, and marital status, we will collect data on education level, occupation, and family income, as per the scale's criteria(18).

Once we collect the responses, we will use MS Excel for data entry and analyze the data using SPSS version 29.

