7.8 Study variables

Dependent Variable:

- **Adherence to Secondary Prevention Medications (SPMs):** This includes adherence levels to specific medications such as antiplatelets, statins, beta-blockers, and ACE inhibitors/ARBs, measured through MYMEDS questionnaire.

Independent Variables:

1. Demographic Factors:

- Age
- Gender
- Education Level
- Occupation
- Place of Residence (Rural vs. Urban)
- Monthly Income

2. Clinical Characteristics:

- Type of Acute Coronary Syndrome (e.g., STEMI, NSTEMI, Unstable Angina)
- Comorbidities (e.g., Hypertension, Diabetes Mellitus, Dyslipidemia, Chronic Kidney Disease)

3. Patient-Reported Factors:

- Concerns about medication side effects
- Pill burden (number of medications)
- Practical issues with medication administration (e.g., difficulties opening bottles)
- Difficulty integrating medications into daily routines

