7.10 Tools and techniques for data collection

- Tools:

Questionnaire

The questionnaire is composed of six simple-to-complete sections.

Section 1:

- Patients provide essential contextual information about the medicines they are taking, when they are administered each day, and their understanding of why they are taking them.
- This helps clinicians compare a patient's actual medication usage with documented clinical records and uncover any medication changes since discharge.

Subsequent sections (Section 2-6):

- These sections use Likert scales instead of binary yes/no responses, which improves the quality of information gathered.
- For example, it allows the assessment of the frequency of non-adherence behaviors rather than just detecting non-adherence.

Section 2:

- Explores overall understanding and satisfaction with medicines.
- Patients respond to four statements regarding their understanding of why their medicines were prescribed and how well they think they are working, using a four-point Likert scale (strongly agree, agree, disagree, strongly disagree).

Sections 3–5:

- Assess specific modifiable barriers to adherence, using the same four-point Likert scale as section 2.
- A free-text box allows patients to specify which medicines their concerns involve.

Section 3:

- Explores three areas of anxiety about medicines (e.g., concerns about medicines causing more harm than good or feeling there are too many medicines).

Section 4:

- Examines four practical concerns associated with medicine-taking (e.g., difficulties with swallowing pills or obtaining repeat prescriptions).

Section 5:

- Assesses three issues related to fitting medicines into the patient's daily routine (e.g., forgetfulness or inconvenience).
- These issues are linked to non-adherence and can potentially be addressed in clinical practice.

Section 6:

- Focuses on adherence to each individual secondary prevention medication (SPM) over the past month.
- It uses a modified version of the SQ tool and a five-point Likert scale.
- Patients are considered non-adherent if they select any answer other than 'all of the time' for any SPM.

[figure not shown]
Technique:

- A relevant questionnaire will be developed and distributed to our research team. They will visit cardiology outpatient department (OPD) as well as in the cardiology ward in Manmohan

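### Section 7.6 gives two values for its one proportion, prints a substitution that equals 259.8 rather than 106.39, and takes its adherence rate from a different instrument without a range

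*Combined protocol and SAP*

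**What the plan says.** Section 7.6 sets a 95% confidence level and a 5% margin of error. It also states that "the response distribution is 50%, and the prevalence of adherence to medication is 92.5" per cent. It then gives Cochran's formula, n = z² × p × q / d², which contains one proportion, and declares z = 1.96, p = 0.925 and d = 0.05. The worked line that follows is "n = [1.96^2 * 0.924 * (1 - 0.817) / (0.05)^2] = 106.39". The result is taken as 106 and raised to 117 for 10% non-response.

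The section names the source of its rate: a 2018 study at another Nepali heart centre, "which reported that 92.5% of respondents were highly adherent to medication" on the four-item MGL scale.

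This study measures its outcome differently. Section 7.8 defines the dependent variable as follows: "This includes adherence levels to specific medications such as antiplatelets, statins, beta-blockers, and ACE inhibitors/ARBs, measured through MYMEDS questionnaire". Section 7.10 gives the classification rule for Section 6 of the questionnaire: "Patients are considered non-adherent if they select any answer other than 'all of the time' for any SPM".

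The background describes lower adherence. Section 2 (Project summary) says that "adherence to prescribed medications remains low, especially in low- and middle-income countries like Nepal". Section 3 (Introduction) cites reports that, by 12 months, "adherence to cardioprotective therapy had dropped to less than 50% across several classes of drugs including statins and ACE-Inhibitors".

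**The concern.** There are three separate defects in one short section.

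- **Two values for one quantity.** The formula has room for a single p. The 50% is neither defined nor used anywhere else, so a reader may believe that the conservative choice of 50% was applied when it was not.
- **A substitution that does not give its own answer.** The worked line uses one proportion for p and the complement of another for q. Neither is the declared 0.925.
- **A rate from another instrument.** A high-adherence share on the MGL scale is carried over to a MYMEDS rule under which one imperfect answer for one drug makes the patient non-adherent. Among patients taking several secondary prevention drugs, the share adherent to all of them cannot exceed the share adherent to any one of them. The documents do not justify the transfer, give an expected MYMEDS rate or show a range.

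The level of adherence is the first specific objective (Section 5b), and the 5-point margin is the only precision target stated for it. A reader who recalculates gets 107, 260 or 385 patients, depending on which printed figure is trusted. If MYMEDS adherence is lower than 92.5%, the main estimate will be less precise than the protocol says.

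**Working it through.** **Inputs.** From Section 7.6: z = 1.96 (z² = 3.8416), d = 0.05 (d² = 0.0025), declared p = 0.925, listed alternative 0.50, printed values 0.924 and 1 − 0.817 = 0.183, and non-response 10%. Adherence rates of 90%, 80% and 70% below are assumptions for illustration. The documents give no MYMEDS rate.

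**Step 1: the plan's own figure.** With the declared p:

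n = 3.8416 × 0.925 × 0.075 / 0.0025 = 106.60

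This agrees with the stated 106.39 and 106 to within rounding, although strictly it rounds up to 107. The inflation is 106 × 1.10 = 116.6, which gives 117. The stated target is therefore reproduced.

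**Step 2: the substitution as printed.**

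n = 3.8416 × 0.924 × 0.183 / 0.0025 = 259.83

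This is about 2.4 times the printed 106.39. Using either printed proportion with its own complement does not recover 106.39:

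- 0.924 × 0.076 gives n = 107.91
- 0.817 × 0.183 gives n = 229.74

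**Step 3: the 50%.**

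n = 3.8416 × 0.50 × 0.50 / 0.0025 = 384.16, so 385

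The 50% therefore plays no part in the stated size.

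**Step 4: the margin if adherence is not 92.5%.** Approximate 95% half-width = 1.96 × √(p(1 − p)/n), in percentage points:

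| Adherence p | n needed for ±5 points | Half-width, 106 respondents | Half-width, 117 respondents |
|---|---|---|---|
| 0.925 | 106.6 | 5.01 | 4.77 |
| 0.90 | 138.3 | 5.71 | 5.44 |
| 0.80 | 245.9 | 7.61 | 7.25 |
| 0.70 | 322.7 | 8.72 | 8.30 |
| 0.50 | 384.2 | 9.52 | 9.06 |

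**Step 5: the adherence rate needed for ±5 points.** Setting the half-width to 0.05 gives p(1 − p) = 0.0025 × n / 3.8416. Since the planned rate is high, the upper root applies:

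- n = 106: p(1 − p) = 0.0690, so p = 0.9255
- n = 117: p(1 − p) = 0.0761, so p = 0.9170

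The planned margin has almost no slack. Even if all 117 respond, it needs adherence of about 91.7% or more.

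**The case against.** The strongest reply is that nothing operational is wrong. Section 7.6 declares p = 0.925, that value yields the target, and 117 appears consistently in the project summary and the sample-size section. Even 106.39 may be sound: an unrounded rate of 0.92516, which rounds to 92.5%, gives it exactly. On this view the defect is two mistyped values and one stray assumption. This stands for the first two defects. They are drafting errors, and neither 260 nor 385 should be read as the required sample size. The printed equation is nevertheless false and needs correcting.

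A second reply is that the 92.5% is a disclosed planning assumption from a Nepali heart centre and that the documents offer no better figure. The contrary evidence is indirect: the project summary gives no number, and the introduction cites general literature by drug class at 12 months, while MYMEDS asks about the past month. This is fair. The documents do not show that 92.5% is wrong for MYMEDS. What is missing is a reason for using it under a different rule, or a range, when the margin depends so closely on it.

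Third, Section 7.3 puts the population at around 1000, so a finite population correction would narrow the margins. The plan's formula applies none, and convenience sampling makes one debatable. Multiplying by √((1000 − 106)/999) = 0.946, the half-widths with 106 respondents become 4.7 points at 92.5%, 7.2 at 80% and 9.0 at 50%. The margin at lower rates stays well above 5.

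Two smaller remarks also stand. Rounding up to 107 and adding 10% gives 117.7, or 118, a difference of one patient. Estimates for a single drug class will have their own denominators, so the 106-respondent margins apply to the overall any-drug classification.

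**Conclusion.** The concern holds on all three points and should be fixed. The printed substitution equals 259.8, not 106.39. The listed 50% is unused and would imply 385 patients if taken as p. Neither changes enrolment, because the declared 92.5% supports 106 and hence 117 to within rounding.

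The transfer of the MGL rate to the MYMEDS rule is the point with a practical consequence. The 5-point margin needs adherence of about 92.5% with 106 respondents or 91.7% with 117; at an assumed 80% it would be 7.6 or 7.2 points. These figures rest on the normal approximation, no finite population correction (as in the plan's formula) and random error only. Section 7.5 itself notes that "Convenience sampling is a non-probability method", so no such margin covers selection.

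No test or decision threshold depends on the 5-point margin. The stated basis and precision need correcting, but the study is not invalidated.

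**What to change.** Keep the enrolment target at 117 and amend Section 7.6 in three places.

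1. Delete the 50% response-distribution assumption.
2. Replace the worked line with 1.96² × 0.925 × (1 − 0.925) / 0.05² = 106.6. Strictly this rounds up to 107; the target of 117 can stand if the margin is described as about 5 points.
3. Add a statement such as:

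> The 92.5% is an MGL rate, and the MYMEDS rate under the any-SPM rule is unknown. With 106 respondents the approximate 95% half-width, without a finite population correction, is 5.0 points at 92.5%, 5.7 at 90%, 7.6 at 80%, 8.7 at 70% and at most 9.5 (at 50%). Rates below 92.5% are assumed for illustration. These margins cover random error only, because sampling is by convenience.

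The cost is wording in one section, with no extra patients or data. The drawback is that the stated precision becomes less favourable.

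### Minor: section 7.6 rounds 106.60 down to 106 and adds 10%, so 117 patients approached yield about 105 respondents, one short of the stated 106 and two short of 107

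*Combined protocol and SAP*

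**What the plan says.** Section 7.6 (Sample size) uses Cochran's formula for a single proportion, with z = 1.96, an assumed adherence proportion of 0.925 and an absolute margin of 0.05. The substituted line reads, in part, "0.924 * (1 - 0.817) / (0.05)^2] = 106.39". The result is rounded to 106, and the section concludes: "The sample size needed for the study is 106 participants".

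The non-response step is introduced as "adding a 10% non-response rate by using the following formula", but the only formula displayed is the Cochran calculation. The step itself is given in words: "By adding 10% non-response, the sample size is increased to 117 participants". The opening sentence of 7.6 also gives 117 as the study's sample size.

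The project summary (section 2) states the purpose of the 117: "targeting approximately 117 patients to account for non-responses". Nowhere does the document divide by one minus the non-response rate.

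**The concern.** A non-response allowance is meant to leave the required number of respondents after the expected losses. Read with the summary, 106 is the number of responses needed and 117 the number targeted before non-response. A 10% loss applies to the 117, not to the 106, so adding 10% of 106 does not quite restore 106.

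The base has a second small slip in the same direction. A sample size computed as a minimum is rounded up, and here a value above 106 was rounded down.

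What is at stake is the internal consistency of the plan's main quantitative commitment, and a clear figure for the team to recruit to. The precision of the adherence estimate is barely affected.

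**Working it through.** **Inputs, all from section 7.6:** z = 1.96; p = 0.925; d = 0.05; requirement 106; non-response 10%; final size 117.

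**1. The plan's own final figure.** 106 x 1.10 = 116.6, rounded up to 117. This reproduces the stated number, so the allowance was added to the base.

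**2. The base.** n = z² x p x (1 − p) / d² = 3.8416 x 0.925 x 0.075 / 0.0025 = 106.60. The plan prints 106.39. Either value rounds up to 107; the plan takes 106.

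**3. The printed working line.** 3.8416 x 0.924 x (1 − 0.817) / 0.0025 = 3.8416 x 0.924 x 0.183 / 0.0025 = 259.8. The two proportions in that line do not match each other or the listed p = 0.925, and they do not give the printed 106.39.

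**4. Respondents expected from 117.** 117 x 0.90 = 105.3, about 105. That is 1 below 106 and 2 below 107.

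**5. Number to approach so that the requirement remains after 10% loss.**
- For 106: 106 / 0.90 = 117.8, so 118 (check: 118 x 0.90 = 106.2).
- For 107: 107 / 0.90 = 118.9, so 119 (check: 119 x 0.90 = 107.1).

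**6. Effect on precision.** Half-width = 1.96 x √(0.925 x 0.075 / n).

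| Respondents | Half-width |
|---|---|
| 105 | 5.04% |
| 106 | 5.01% |
| 107 | 4.99% |

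The stated requirement of 106 already sits just above 5%. The non-response step adds about 0.02 to 0.03 percentage points (5.04 against 5.01).

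**The case against.** The strongest reply is that nothing of substance changes. A margin of 5.04% rounds to the stated 5%, and the planning proportion matters more: with 106 respondents, p = 0.92 gives 1.96 x √(0.92 x 0.08 / 106) = 5.16% and p = 0.93 gives 1.96 x √(0.93 x 0.07 / 106) = 4.86%. That is right, and it is why the point is minor.

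The plan also did what it said. It announced that 10% would be added, and it added 10%. A reader might infer that the plan broke its own rule, but the text does not support that. The criticism is of the rule chosen, which falls slightly short of its purpose.

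Two further replies stand only in part:

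- **117 may mean completed interviews.** Section 7.6 speaks of participants, section 7.7 makes consent an inclusion criterion, and under section 7.5 the researcher puts the questions in person to a convenience sample, so one more interview would close the gap. However, section 2 ties 117 to non-responses. Section 11 lets participants skip questions, and section 10 refers to excluding patients with incomplete records. Neither loss has an allowance of its own.
- **The population is finite.** Section 7.3 puts it at around 1000. With a finite population correction the need would be 106.60 / (1 + 105.60/1000) = 96.4, so 97, and 105 respondents would suffice. The plan applies no such correction, so this does not reconcile 117 with its own 106.

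**Conclusion.** The point holds as a minor inconsistency. If 10% of the 117 approached do not respond, about 105 respondents are expected: one short of the stated 106 and two short of the 107 that the formula requires at p = 0.925. The expected margin is about 5.04%.

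A reader might go further and infer that the study is undersized or fails to deliver its 5% margin. The figures do not support that: the excess is 0.04 percentage points. Nor does the 259.8 from the working line show that about 260 respondents are needed. The listed proportion is 0.925, and the printed result of 106.39 is close to the 106.60 it gives, so the substituted values look like a transcription fault.

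The conclusion assumes that 117 counts patients before non-response, as section 2 indicates, that the 10% applies to those approached, and that p = 0.925 is the intended input. Section 7.6 also lists a response distribution of 50%. At p = 0.5 the same formula gives 3.8416 x 0.25 / 0.0025 = 384.16, so 385. The plan's result does not rest on that value, but its presence should be explained or removed.

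**What to change.** Choose one of two statements:

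- **Keep 117 as the number approached**, and state that about 105 respondents are expected, giving a margin of about 5.04%.
- **Restate the requirement as 107 respondents**, and the number approached as 107 / 0.9 = 118.9, so 119.

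Make the change consistently in the first and last sentences of 7.6, in its lines giving the rounded n and the 106 needed, and in the section 2 summary. Say explicitly whether the final figure counts patients approached or questionnaires completed. In the same edit, replace the working line by 1.96² x 0.925 x 0.075 / 0.05² = 106.60.

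The cost is a few figures in two sections. The first option adds no patients and the second at most two. Neither alters the design.
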